## **6.2 Management of toxicity (other than hand-foot skin reaction, hypertension and LFT abnormalities)**

The table below outlines dose adjustments for **most hematologic and non-hematologic toxicities related to regorafenib** except hand-foot skin reaction (HFSR) and hypertension and LFT abnormalities.

In addition to these recommended dose modifications, subjects who develop diarrhea (see

Section 6.6), mucositis, anorexia or other events predisposing to fluid loss or inadequate fluid intake should be carefully monitored and rehydrated as clinically necessary. This is in order to minimize the risk of postural hypotension and renal failure.

**Table 6.2 Recommended dose modification for most toxicities, except hand-foot skin reaction, hypertension and ALT/AST/bilirubin**

NCI-CTCAE v 4.03 a	Dose Interruption	Dose Modification b	Dose for Subsequent Cycles
Grade (G) 0-2	Treat on time	No change	No change
G 3	Delay until $\leq$ G 2 c	Reduce by 1 dose level	If toxicity remains < G2, dose re-escalation can be considered at the discretion of the treating investigator. If dose is re-escalated and toxicity ( $\geq$ G3) recurs, institute permanent dose reduction.
G 4	Delay until $\leq$ G 2 c	At a minimum, reduce by 1 dose level.  Strongly consider permanent discontinuation for G4 events such as: gastrointestinal perforation/fistula, severe or life-threatening hemorrhage, reversible posterior leukoencephalopathy syndrome, or wound dehiscence.	

a. G: Grade; NCI-CTCAE = National Cancer Institute - Common Terminology Criteria for Adverse Events, version 4.03
 
b. Excludes alopecia, non-refractory nausea/vomiting, non-refractory hypersensitivity and nonclinical and asymptomatic laboratory abnormalities.
 
c. If no recovery after a 4 week delay, treatment should be permanently discontinued unless subject is deriving clinical benefit and is discussed with the SARC Medical Officer.
			

### 6.3 Management of hand-foot skin reaction

**At first occurrence of HFSR, independent of grade, prompt institution of supportive measures such as topical emollients, low potency steroids, or urea-containing creams should be administered.**

Grading and dose alterations are noted in Tables 6.3 and 6.4 below.

Recommended prevention/management strategies for skin toxicities consistent with HFSR are summarized below:

### Control of calluses

Before initiating treatment with regorafenib:

- Check condition of hands and feet
- Suggest a manicure/pedicure, when indicated
- Recommend pumice stone use for callus or ‘rough spot’ removal.

During regorafenib treatment:

- Avoid pressure points
- Avoid items that rub, pinch or create friction.

### Use of creams

Non-urea based creams may be applied liberally

- Keratolytic creams (e.g. urea-based creams, salicylic acid 6%) may be used sparingly and only to affected (hyperkeratotic) areas
- Alpha hydroxyl acids (AHA) based creams may be applied liberally 2 times a day. Approximately 5% to 8% provides gentle chemical exfoliation
- Topical analgesics (e.g. lidocaine 2%) are to be considered for pain control
- Topical corticosteroids like clobetasol 0.05% should be considered for subjects with G 2 or 3 HFSR. Avoid systemic steroids.

### Tender areas should be protected as follows:

- Use socks/gloves to cover moisturizing creams
- Wear well-padded footwear
- Use insole cushions or inserts (e.g. silicon, gel)
- Foot soaks with tepid water and Epson salts.

**Table 6.3.1 Grading for Hand-Foot Skin Reaction**

	G 1	G 2	G 3
NCI-CTCAE v 4.03 Palmar-plantar erythrodysesthesia syndrome(a)	Minimal skin changes or dermatitis (e.g., erythema, edema, or hyperkeratosis) without pain	Skin changes (e.g., peeling, blisters bleeding, edema, or hyperkeratosis) with pain	Severe skin changes (e.g., peeling, blisters, bleeding, edema, or hyperkeratosis) with pain
Further description / examples of skin	Numbness, dysesthesia / paresthesia tingling,	Painful erythema and swelling of the hands	Moist desquamation, ulceration, blistering,

changes	painless swelling, or erythema of the hands and/or feet	and/or feet	or severe pain of the hands and/or feet
Effect on activities	Does not disrupt normal activities	Limiting instrumental activities of daily life (e.g., preparing meals, shopping for groceries or clothes, using the telephone, managing money)	Limiting self-care activities of daily life (e.g., bathing, dressing and undressing, feeding self, using the toilet, taking medications) and not bedridden
(a) Palmar-plantar erythrodysesthesia syndrome is a disorder characterized by redness, marked discomfort, swelling, and tingling in the palms of hands or the soles of the feet. G: grade			

**Table 6.3.2 Recommended dose modification for hand-foot-skin reactiona**

Grade of event (NCI-CTCAE v 4.03)	Occurrence	Suggested Dose Modification
Grade (G) 1	Any	Maintain dose level and immediately institute supportive measures for symptomatic relief
G 2	1 st occurrence	Consider decreasing dose by one dose level and immediately institute supportive measures. If no improvement, interrupt therapy for a minimum of 7 days, until toxicity resolves to G 0-1 b, c
	No improvement within 7 days or 2 nd occurrence	Interrupt therapy until toxicity resolves to G 0-1. c When resuming treatment, decrease dose by one dose level b
	3 rd occurrence	Interrupt therapy until toxicity resolves to G 0-1. c When resuming treatment, decrease dose by one dose level. b, d
	4 th occurrence	Discontinue therapy
G 3	1 st occurrence	Institute supportive measures immediately. Interrupt therapy for a minimum of 7 days until toxicity resolves to G 0-1. c When resuming treatment, decrease dose by one dose level. b, d
	2 nd occurrence	Institute supportive measures immediately. Interrupt therapy for a minimum of 7 days until toxicity resolves to G 0-1. c When resuming treatment, decrease dose by one additional dose level b, d
	3 rd occurrence	Discontinue treatment permanently.

a. More conservative management is allowed if judged medically appropriate by the investigator.
 
b. If toxicity returns to G 0-1 after dose reduction, dose re-escalation is permitted at the discretion of the investigator if subject has completed one cycle at reduced dose without recurrence of event.
 
c. If there is no recovery after a 4 week delay, treatment with regorafenib or placebo will be discontinued permanently.
 
d. Subjects requiring > 2 dose reductions should go off protocol therapy.
 
e. The maximum daily dose is 160 mg
		

## 6.4 Hypertension

Hypertension is a recognized AE associated with regorafenib treatment. Subject will have their blood pressure measured at least weekly at the study site on weeks 1, 2, 3, 5, and 7. If additional blood pressure measurements are done outside the study site, and the blood pressure is > 140 mm Hg systolic or > 90 mm Hg diastolic (NCI CTCAE v 4.03), then the subject must contact study personnel. The management of hypertension, including the choice of antihypertensive medication, will be performed according to local standards and to the usual practice of the investigator. Every effort should be made to control blood pressure by medical means other than study drug dose modification. If necessary, **Table 6.5** below outlines suggested dose reductions.

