Fifteen subjects (36.6%) experienced drug-related TEAEs of worst CTCAE severity Grade  $\geq 3$ , with 11 subjects (26.8% of 41) and 4 subjects (9.8%) having drug-related TEAEs of worst Grades 3 and 4, respectively. Drug-related TEAEs of CTCAE Grade 5 did not occur. Common drug-related TEAEs of CTCAE Grade 3 or above (Grades 3/4), occurring in  $\geq 5\%$  of all 41 treated subjects (by MedDRA preferred term) were thrombocytopenia and rash maculo-papular (7.3% each).

Dose-limiting toxicities were thrombocytopenia at 60 mg/m^2, rash maculopapular at 72 mg/m^2, fever at 82 mg/m^2, and hypertension and erythroderma at 93 mg/m^2. An increased incidence of Grades 3/4 hematological events was observed across dose levels; it appeared that subjects with a history of myelosuppressive therapies such as high dose chemotherapy with stem cell rescue or craniospinal irradiation were at a higher risk for such events.

Overall, 27 out of 41 subjects (65.9%) had at least one dose modification, and the majority of dose modifications were due to AEs; 14 dose reductions (34.1%) were reported for the 41 subjects treated. No subject had more than one dose reduction. Three out of 6 subjects (50.0%), 10 out of 14 subjects (71.4%), 7 out of 14 subjects (50.0%), and 6 out of 7 subjects (85.7%) had AEs leading to dose interruptions in Dose Levels 1, 2, 3 and 4, respectively. The most commonly reported TEAEs (any grade) leading to interruption of study drug in at least 5% subjects of any dose level were pyrexia, platelet count decreased, and rash maculo-papular (7.3% of each). The median duration of regorafenib treatment interruptions or delays (excluding the protocol defined 7 days rest period) was 4 days (range: 1-17 days).

Pharmacokinetics: Regorafenib exposure at all dose levels (60, 72, 82 and 93 mg/m^2) was comparable to that observed in adults; including high inter-subject variability. The observed geometric mean exposure for the 82 mg/m^2 dose group of 50.1 and 47.8 (mg\*h/L), based on nominal and actual dosing, is in the same range as that observed (48.4 mg\*h/L) in adults at the dose level of 160 mg q.d.

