- 3.2.10 Uncontrolled hypertension (systolic pressure  $> 140$  mm Hg or diastolic pressure  $> 90$  mm Hg [NCI-CTCAE v 4.03] on repeated measurement) despite optimal medical management. Uncontrolled hypertension for this study will be defined as greater than 95th percentile for age on two anti-hypertensives.
- 3.2.11 Active or clinically significant cardiac disease including:

- 1) Congestive heart failure–New York Heart Association (NYHA) > class II.
  - 2) Active coronary artery disease.
  - 3) Cardiac arrhythmias requiring anti-arrhythmic therapy other than beta blockers or digoxin.
  - 4) Unstable angina (anginal symptoms at rest), new onset angina within 3 months before randomization, or myocardial infarction within 6 months before randomization.
- 3.2.12 Evidence or history of bleeding diathesis. Patients on warfarin, heparinoids, or factor X inhibitors are permitted on study.
- 3.2.13 Any hemorrhage or bleeding event  $\geq$  NCI CTCAE Grade 3 within 4 weeks prior to study registration.
- 3.2.14 Subjects with thrombotic, embolic, venous, or arterial events, such as cerebrovascular accident (including transient ischemic attacks) deep vein thrombosis or pulmonary embolism within 6 months of start of study treatment.
- 3.2.15 Known history of human immunodeficiency virus (HIV) infection or current chronic or active hepatitis B or C infection requiring treatment with antiviral therapy.
- 3.2.16 Ongoing infection > Grade 2 NCI-CTCAE v 4.03.
- 3.2.17 Presence of a non-healing wound, non-healing ulcer, or benign bone fracture (patients with stress insufficiency fractures e.g. from osteoporosis or pathological fracture from tumor are eligible for study).
- 3.2.18 Patients with seizure disorder requiring medication.
- 3.2.19 Proteinuria > 100 mg/dl on urine analysis.
- 3.2.20 Interstitial lung disease with ongoing signs and symptoms at the time of informed consent.
- 3.2.21 Pleural effusion or ascites that causes respiratory compromise ( $\geq$  NCI-CTCAE version 4.03 Grade 2 dyspnea).
- 3.2.22 History of organ allograft (including corneal transplant).
- 3.2.23 Known or suspected allergy or hypersensitivity to regorafenib, or excipients of the formulations given during the course of this trial.
- 3.2.24 Any malabsorption condition.

- 3.2.25 Women who are pregnant or breast-feeding.
- 3.2.26 Any condition which, in the investigator's opinion, makes the subject unsuitable for trial participation.

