**Table 6.4.2 Management of Treatment Emergent Hypertension for pediatric patients**

**Please refer to appendix:**

Grade (CTCAE v 4.03)	Antihypertensive Therapy	Regorafenib or placebo Dosing
Grade 1 If age ≤ 17 years: Asymptomatic, transient (< 24 hrs) BP increase > ULN; intervention not indicated. If age > 17	Consider increased BP monitoring; start anti-hypertensive medication if appropriate	No modification

years: (SBP 120-139 mmHg or DBP 80-89 mmHg)		
Grade 2 asymptomatic If age ≤ 17 years: Recurrent or persistent (≥ 24 hrs) BP > ULN; If age > 17 years: (SBP 140-159 mmHg or DBP 90-99 mmHg)	-If age ≤ 17 years: monotherapy indicated, -If age > 17 years: As in Table 6.5	Continue Study drug
Grade 2 symptomatic OR Grade 3: (> 17 years: SBP > 160 mmHg or DBP > 100 mmHg) requiring more than one drug or more intensive therapy than previously (all ages)	• Start or adjust anti-hypertensive medication as in table 6.5	• Hold study drug until symptoms resolve AND BP < 95th percentile ULN for age, height, and gender, if age ≤ 17 years; or BP < 160/90 mmHg if age > 17 years. Resume study at 100% (full) dose. If similar toxicity recurs, discontinue study drug.
Grade 4 (all ages) life threatening (eg, hypertensive crisis or malignant hypertension)	Per institutional guidelines	Discontinue study drug

**90th and 95th PERCENTILE BLOOD PRESSURE BY PERCENTILE HEIGHT IN  
GIRLS AGE 1-17 YEARS**

Age (Year)	BP Percentile	Systolic BP (mmHg)							Diastolic BP (mmHg)						
		Percentile of Height							Percentile of Height						
↓		5th	10th	25th	50th	75th	90th	95th	5th	10th	25th	50th	75th	90th	95th
1	90th	97	97	98	100	101	102	103	52	53	53	54	55	55	56
	95th	100	101	102	104	105	106	107	56	57	57	58	59	59	60
2	90th	98	99	100	101	103	104	105	57	58	58	59	60	61	61
	95th	102	103	104	105	107	108	109	61	62	62	63	64	65	65
3	90th	100	100	102	103	104	106	106	61	62	62	63	64	64	65

	95th	104	104	105	107	108	109	110	65	66	66	67	68	68	69
4	90th	101	102	103	104	106	107	108	64	64	65	66	67	67	68
	95th	105	106	107	108	110	111	112	68	68	69	70	71	71	72
5	90th	103	103	105	106	107	109	109	66	67	67	68	69	69	70
	95th	107	107	108	110	111	112	113	70	71	71	72	73	73	74
6	90th	104	105	106	108	109	110	111	68	68	69	70	70	71	72
	95th	108	109	110	111	113	114	115	72	72	73	74	74	75	76
7	90th	106	107	108	109	111	112	113	69	70	70	71	72	72	73
	95th	110	111	112	113	115	116	116	73	74	74	75	76	76	77
8	90th	108	109	110	111	113	114	114	71	71	71	72	73	74	74

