### 90th and 95th PERCENTILE BLOOD PRESSURE BY PERCENTILE HEIGHT IN BOYS AGE 1-17 YEARS

Age (Year)	BP Percentile ↓	Systolic BP (mmHg)							Diastolic BP (mmHg)						
		Percentile of Height							Percentile of Height						
		5th	10th	25th	50th	75th	90th	95th	5th	10th	25th	50th	75th	90th	95th
1	90th	94	95	97	99	100	102	103	49	50	51	52	53	53	54
	95th	98	99	101	103	104	106	106	54	54	55	56	57	58	58
2	90th	97	99	100	102	104	105	106	54	55	56	57	58	58	59
	95th	101	102	104	106	108	109	110	59	59	60	61	62	63	63
3	90th	100	101	103	105	107	108	109	59	59	60	61	62	63	63
	95th	104	105	107	109	110	112	113	63	63	64	65	66	67	67

4	90th	102	103	105	107	109	110	111	62	63	64	65	66	66	67
	95th	106	107	109	111	112	114	115	66	67	68	69	70	71	71
5	90th	104	105	106	108	110	111	112	65	66	67	68	69	69	70
	95th	108	109	110	112	114	115	116	69	70	71	72	73	74	74
6	90th	105	106	108	110	111	113	113	68	68	69	70	71	72	72
	95th	109	110	112	114	115	117	117	72	72	73	74	75	76	76
7	90th	106	107	109	111	113	114	115	70	70	71	72	73	74	74
	95th	110	111	113	115	117	118	119	74	74	75	76	77	78	78
8	90th	107	109	110	112	114	115	116	71	72	72	73	74	75	76
	95th	111	112	114	116	118	119	120	75	76	77	78	79	79	80
9	90th	109	110	112	114	115	117	118	72	73	74	75	76	76	77
	95th	113	114	116	118	119	121	121	76	77	78	79	80	81	81
10	90th	111	112	114	115	117	119	119	73	73	74	75	76	77	78
	95th	115	116	117	119	121	122	123	77	78	79	80	81	81	82
11	90th	113	114	115	117	119	120	121	74	74	75	76	77	78	78
	95th	117	118	119	121	123	124	125	78	78	79	80	81	82	82
12	90th	115	116	118	120	121	123	123	74	75	75	76	77	78	79
	95th	119	120	122	123	125	127	127	78	79	80	81	82	82	83
13	90th	117	118	120	122	124	125	126	75	75	76	77	78	79	79
	95th	121	122	124	126	128	129	130	79	79	80	81	82	83	83
14	90th	120	121	123	125	126	128	128	75	76	77	78	79	79	80
	95th	124	125	127	128	130	132	132	80	80	81	82	83	84	84
15	90th	122	124	125	127	129	130	131	76	77	78	79	80	80	81
	95th	126	127	129	131	133	134	135	81	81	82	83	84	85	85
16	90th	125	126	128	130	131	133	134	78	78	79	80	81	82	82
	95th	129	130	132	134	135	137	137	82	83	83	84	85	86	87
17	90th	127	128	130	132	134	135	136	80	80	81	82	83	84	84
	95th	131	132	134	136	138	139	140	84	85	86	87	87	88	89

Source: Adapted from: The Fourth Report on the Diagnosis, Evaluation, and Treatment of High Blood Pressure in Children and Adolescents; NIH Publication No. 05-5267.

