#### **8.5 Agent Accountability**

All study drugs will be stored at the investigational site in accordance with Good Clinical Practice (GCP) and Good Manufacturing Practices (GMP) requirements and the instructions given by the clinical supplies department of the Institution and will be inaccessible to unauthorized personnel.

Accountability and patient compliance will be assessed by maintaining adequate drug dispensing and return records.

Accurate records must be kept for each study drug provided by the sponsor. The drug dispensing log must be kept current and contain the following information:

- Documentation of drug shipments received from the sponsor (date received and quantity)
- Disposition of unused study drug not dispensed to patient
- The identification of the patient to whom the study medication was dispensed
- The date(s) and quantity of the study medication dispensed to the patient.

All supplies, including partially used or empty containers must be returned to the treating institution at the end of the study, and destroyed as required by local or institutional regulations (Section 8.7). Copies of the dispensing & inventory logs must be sent to SARC (use the address in Section 8.7).

Patients will also keep a Study Drug diary to indicate their compliance with therapy and adverse events they experience. These diaries will be reviewed and collected at each patient visit.

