## **Cycle 3 Week 1, day 1 (Week 9 overall) and later**

Treatment continues 3 weeks on, 1 week off.

Visits every 2 weeks until end of cycle 4, then every 4 weeks.

- Tumor measurements and imaging every 8 weeks for 32 weeks, then every 12 weeks. Scans may be done  $\pm 7$  days of expected date.

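### The only duty to call the site about an out-of-clinic blood pressure is set at >140/>90 mm Hg for every age, well above the level at which the protocol itself treats children

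*Combined protocol and SAP*

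**What the plan says.** Section 6.4 schedules clinic blood pressures in weeks 1, 2, 3, 5 and 7. For readings taken elsewhere it gives one instruction, the same for every subject: if "blood pressure is > 140 mm Hg systolic or > 90 mm Hg diastolic (NCI CTCAE v 4.03), then the subject must contact study personnel".

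Children are held to a different standard:

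- **Table 6.4.2, Grade 2, age 17 or under:** "Recurrent or persistent (≥ 24 hrs) BP > ULN". The listed action is monotherapy, with study drug continued.
- **Table 6.4.2, symptomatic Grade 2 or Grade 3:** drug is held until symptoms resolve and "BP < 95th percentile ULN for age, height, and gender, if age ≤ 17 years". This identifies the upper limit of normal as the 95th percentile.
- **Percentile tables after Table 6.4.2:** the limits are printed in full for girls and boys, the latter under the title "90th and 95th PERCENTILE BLOOD PRESSURE BY PERCENTILE HEIGHT IN BOYS AGE 1-17 YEARS".
- **Exclusion 3.2.10:** the study's definition of uncontrolled hypertension also uses a "percentile for age on two anti-hypertensives".

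The Appendix C diary has a blood-pressure row and asks for a weekly check, but gives no limit and no instruction to call. Section 8.5 says of the diaries: "These diaries will be reviewed and collected at each patient visit". For cycle 3 onward, section 9.2 sets the visits: "Visits every 2 weeks until end of cycle 4, then every 4 weeks". Section 3.1.1 admits children from age 5 to the rhabdomyosarcoma cohort (D) and from age 10 to the others.

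**The concern.** For adults the call rule and the treatment rule agree. Grade 2 in Table 6.4.1 begins at 140 systolic or 90 diastolic, and drug treatment of blood pressure begins at that grade. An adult is therefore told to call at about the level where the site would act. For children the treatment level was moved to the 95th percentile, but the call level stayed at the adult figure.

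The consequence is delay. A family that follows the protocol exactly can record raised readings week after week in the range where Table 6.4.2 indicates treatment, and need tell nobody until the next visit. The readings are not lost, because the diary is reviewed and vital signs are taken at visits.

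Hypertension is one of the synopsis's specific safety concerns, and section 6.4 calls it a recognised regorafenib adverse event. In the paediatric phase I trial (section 2.4.3) it was among the dose-limiting toxicities: "hypertension and erythroderma at 93 mg/m"², one dose level above the 82 mg/m² starting dose used here. The dose-limiting toxicity at 82 mg/m² was fever.

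**Working it through.** **Inputs.** The call level is 140 systolic or 90 diastolic (section 6.4). The child's limit is each printed 95th-percentile value for ages 5 to 17. That gives 13 ages × 7 height columns × 2 sexes = 182 entries, each with a systolic and a diastolic value.

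**Formula.** Systolic gap = 140 − 95th-percentile systolic. Diastolic gap = 90 − 95th-percentile diastolic. A positive gap is a band of readings above the child's limit that creates no duty to call.

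**Result over all 182 entries.**

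| | Median gap (mm Hg) | Range | Entries with no gap |
|---|---|---|---|
| Systolic | 19 | 0–33 | 1 (boys aged 17, tallest column) |
| Diastolic | 10 | 1–21 | 0 |

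The systolic gap is at least 10 mm Hg in 159 of 182 entries.

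**By age (gap in mm Hg, systolic / diastolic).**

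| Age | Girls | Boys |
|---|---|---|
| 5 | 27–33 / 16–20 | 24–32 / 16–21 |
| 10 | 18–24 / 10–13 | 17–25 / 8–13 |
| 17 | 8–15 / 4–8 | 0–9 / 1–6 |

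**Example.** A 5-year-old girl of median height has a limit of 110/72. Repeated home readings of 138/88 are 28 mm Hg systolic and 16 mm Hg diastolic above it and would be Grade 2 under Table 6.4.2. They do not trigger the call.

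**Length of the delay.** Clinic visits fall in weeks 1, 2, 3, 5 and 7, then every 2 weeks to the end of cycle 4 (4 × 28 days = 16 weeks), then every 4 weeks. After week 3 the wait is therefore up to 2 weeks, and from about week 17 up to 4 weeks, apart from the visit window of a few days.

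**How many children.** Cohorts A to C have finished enrolling. Cohorts D and E together have funding for 24 patients, about 12 each, adults included. Ages 5 to 9 can enter only cohort D. With planned 8-week disease control of 10% to 30%, 12 × 0.10 = 1.2 and 12 × 0.30 = 3.6, so about 1 to 4 patients of any age would be controlled at week 8. Some of those may progress before week 17. For most young children the relevant delay is the 2-week one.

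**The case against.** The strongest reply concerns weight.

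- **Few children, short delay.** This stands. The gap statistics also describe table entries, not patients. The documents do not say how many children would record a reading in the band, and perhaps no child aged 5 to 9 would reach the 4-week schedule.
- **Phase I hypertension was not frequent.** This also stands. Hypertension is not among the drug-related events listed at 20% or more of 41 children, nor among the drug-related Grade 3 or higher events listed at 5% or more. Since 5% of 41 is 2.05, that implies at most 2 children with drug-related Grade 3 or higher hypertension.
- **Dose rounding proves little.** At the minimum body surface area of 0.65 m², 82 × 0.65 = 53.3 mg rounds to 60 mg, which is 92.3 mg/m². At 0.84 m², 68.9 mg also rounds to 60 mg, which is 71 mg/m². Rounding moves doses both ways, so the conclusion does not rest on it.
- **Other safeguards exist.** Visits are weekly for the first 3 weeks, the site telephones once on days 4 to 6 of week 1, and a site may set its own call limit. These shorten the exposure, but none gives the family a paediatric level at which to call.
- **A percentile trigger would catch transient rises.** A rise above the limit lasting under 24 hours is only Grade 1 in a child. This does not defeat the fix. The adult rule also fires on a single reading, and the call lets staff tell a transient rise from a persistent one.
- **Instructions may exist elsewhere.** Consent pages were not available for review and the operations manual is not part of the document. Either could contain a call instruction for families, and this cannot be checked.

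**Conclusion.** The concern holds. Section 6.4 states a rule that fits adults and misfires for children: the level at which they must call lies above the level at which the protocol's own table treats them in every printed entry for ages 5 to 17, apart from the systolic value in one. The median excess is 19 mm Hg systolic and 10 mm Hg diastolic. It is largest in the youngest and nearly disappears in tall 17-year-old boys.

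The harm is delayed antihypertensive treatment, mostly by up to 2 weeks, in a small number of children. Adverse event grading is unchanged and no efficacy analysis is touched. It should be fixed because it is a paediatric safety instruction affecting cohorts still to be enrolled under this version, and correcting it is cheap.

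The conclusion assumes that families take the weekly home readings the diary asks for, and that no paediatric call level is given in the consent form or operations manual.

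**What to change.** In section 6.4, add a sentence stating that for subjects aged 17 or under the call level is any outside reading above the 95th percentile for age, height and sex in the printed tables. Keep >140/>90 for those over 17.

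In Appendix C, add a field beside the weekly blood-pressure row where the site writes the child's own systolic and diastolic limits, with an instruction to call if either is exceeded. The site fills it in when handing out the diary each cycle.

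The cost is one sentence and one diary field, using tables already in the protocol, with no new measurement. The downside is some extra calls about readings that prove transient, which the Grade 1 row of Table 6.4.2 already covers.
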